RAPID local ischemic postconditioning in acute ischemic Stroke
pAtients recei**V**Ed successful thrombectomy reperfusion (**RAPID-**
SAVE)

STATISTICAL ANALYSIS PLAN

Principal Investigator

[name], PhD

Shanghai Sixth People's Hospital Affiliated to Shanghai Jiao Tong University School
of Medicine

Clinical Trial: NCT06526429

Protocol Version 1.0

Oct 14, 2024

BOIN12 Study Design and Statistical Analysis Plan

2 This study employed the Bayesian optimal interval phase I/II (BOIN12) trial design¹
3 find the optimal biological dose (OBD). The BOIN12 design used utility to quantify
4 the desirability of a dose in terms of toxicity-efficacy trade off and adaptively
5 allocated patients to the dose that has the highest estimated desirability. The utilities
6 ascribed to each possible efficacy-toxicity outcome were as follows: (No Toxicity,
7 Efficacy) = 100; (Toxicity, Efficacy) = 60; (No Toxicity, No Efficacy) = 40; and
8 (Toxicity, No Efficacy) = 0. A higher value indicated a more desirable outcome (0
9 and 100 present the least and most desirable outcome, respectively).

10 Let u_1, \dots, u_4 denote these utilities. Given a dose j , let p_1, \dots, p_4 denote the
 11 corresponding probabilities of observing each of the possible toxicity-efficacy
 12 outcomes. Then, the mean utility of dose j is

$$uj=p1u1+p2u2+p3u3+p4u4.$$

14 A higher value of uj indicated a higher desirability of dose j in terms of risk-benefit
15 tradeoff. To safeguard patients from toxic and/or futile doses, two dose acceptability
16 criteria were used by BOIN12 to decide which doses might be used to treat patients.
17 A dose was deemed as admissible and eligible for treating patients if it satisfied the
18 following safety and efficacy criteria.

(Safety) $\Pr(\pi T > 0.15 \mid \text{data}) < 0.95$,

(Efficacy) $\Pr(\pi E < 0.6 \mid \text{data}) < 0.9$.

21 where πT and πE were the true DLT rate and efficacy rate, respectively. These two
22 conditions ensured that the admissible dose could not be overly toxic or futile. Doses
23 that were not admissible would be eliminated from the trial. If a dose was eliminated
24 due to toxicity, all doses higher than that dose would also be eliminated. The
25 objective was to identify the OBD, defined as the dose that was admissible and had
26 the highest desirability.

RAPID-SAVE Trial SAP

27 We planned to enrol a maximum number of 60 patients with a cohort size of 5. When

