28 the current dose's observed toxicity rate fell within the stay interval of BOIN, we
29 would stop exploring higher doses if its number of patients $\geq N^*$, where $N^* = 5$. The
30 BOIN12 design is depicted in Supplemental Figure 1 and it was implemented
31 according to the following 3 steps via the BOIN12 shiny app².

32 1. Treat the first cohort at dose level 3.
33 2. Suppose that the current dose level is j , choose one of the following three
34 cases to determine the dose for treating the next cohort of patients:

35 **Case A:** determine the desirability of dose levels $j-1$, j , and $j+1$ using the
36 rank-based desirability score (RDS) table (Table 1), and choose the one that
37 has the highest desirability to treat the next cohort. If the RDS of all three
38 doses are “E,” stop the trial and no dose should be selected. In the case that
39 dose level $j-1$ (or $j+1$) does not exist, then apply the above rule to dose
40 levels j and $j+1$ (or j and $j-1$).

41 **Case B:** determine the desirability of dose levels j and $j-1$ using the RDS
42 table (Table 1), and choose the one that has the higher desirability to treat the
43 next cohort. If the RDS of the two doses are “E,” stop the trial and no dose
44 should be selected. If the current dose level j is the lowest dose, treat the next
45 cohort of patients at the lowest dose unless the RDS of the lowest dose is “E,”
46 at which point terminate the trial.

47 **Case C:** determine the desirability of dose levels j and $j-1$ using the RDS
48 table (Table 1).

49

- 50 ○ If the current dose level j is the lowest dose, treat the new patients at
51 the lowest dose unless the RDS of the lowest dose is “E,” at which
 point terminate the trial.

52 ○ If the current dose level j is not the lowest dose and the RDS of dose
53 level $j-1$ is not “E,” de-escalate the dose to level $j-1$ to treat the next
54 cohort of patients.

55 If the current dose level j is not the lowest dose and the RDS of dose
56 level $j-1$ is “E,” stay at the current dose level j to treat the next cohort of
57 patients unless the RDS of dose level j is “E,” at which point terminate the
58 trial. In the event of **Case A** or **Case B**, to prevent getting stuck in a local
59 dose, an extra dose exploration rule is implemented to escalate to the next
60 higher untried dose if the following two conditions are met:

61 ○ The number of patients treated at the current dose is ≥ 15 .

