62 ○ The next higher dose is not eliminated and has never been used for
63 treating patients.

64 3. Repeat step 2 until the maximum sample size of 60 is reached or if the number
65 of patients treated on any dose reaches 20. Then, use the isotonic estimation
66 method described in Lin et al.¹ to select the OBD as the dose that is admissible
67 and that has the highest estimated utility.

[figure not shown]

Figure 1. Flowchart for trial conduct using the BOIN12 design, where $N^*=5$,

and $(\lambda_e, \lambda_d) = (0.118, 0.179)$.

eTable 1. Rank-based desirability score (RDS) table for the BON12 design, where “E” means elimination. A larger value of RDS means higher desirability, and any value of RDS is deemed higher than “E”. #Pts denotes the number of evaluable patients treated at current dose; #Tox denotes the number of evaluable patients who experience toxicity; #Eff denotes the number of evaluable patients who experience efficacy.

#Pts	#Tox	#Eff	RDS												
0	0	0	262	15	0	7	96	15	4	9	61	20	2	19	528
5	0	<= 1	E	15	0	8	159	15	4	10	115	20	2	20	556
5	0	2	169	15	0	9	232	15	4	11	183	20	3	<= 9	E
5	0	3	268	15	0	10	297	15	4	12	256	20	3	10	19
5	0	4	377	15	0	11	366	15	4	13	321	20	3	11	47
5	0	5	483	15	0	12	435	15	4	14	389	20	3	12	90

RAPID-SAVE Trial SAP

#Pts	#Tox	#Eff	RDS												
5	1	<= 1	E	15	0	13	497	15	4	15	457	20	3	13	147
5	1	2	101	15	0	14	542	15	>= 5	Any	E	20	3	14	213
5	1	3	199	15	0	15	565	20	0	<= 9	E	20	3	15	264
5	1	4	308	15	1	<= 6	E	20	0	10	90	20	3	16	328
5	1	5	413	15	1	7	61	20	0	11	147	20	3	17	391
5	>= 2	Any	E	15	1	8	115	20	0	12	213	20	3	18	448
10	0	<= 4	E	15	1	9	183	20	0	13	264	20	3	19	501
10	0	5	172	15	1	10	256	20	0	14	328	20	3	20	539

RAPID-SAVE Trial SAP

#Pts	#Tox	#Eff	RDS												
10	0	6	250	15	1	11	321	20	0	15	391	20	4	<= 9	E
10	0	7	330	15	1	12	389	20	0	16	448	20	4	10	8
10	0	8	414	15	1	13	457	20	0	17	501	20	4	11	27
10	0	9	492	15	1	14	514	20	0	18	539	20	4	12	59
10	0	10	545	15	1	15	550	20	0	19	561	20	4	13	109
10	1	<= 4	E	15	2	<= 6	E	20	0	20	571	20	4	14	170
10	1	5	117	15	2	7	31	20	1	<= 9	E	20	4	15	227
10	1	6	196	15	2	8	75	20	1	10	59	20	4	16	287

RAPID-SAVE Trial SAP

#Pts	#Tox	#Eff	RDS												
10	1	7	286	15	2	9	136	20	1	11	109	20	4	17	351
10	1	8	360	15	2	10	204	20	1	12	170	20	4	18	410
10	1	9	444	15	2	11	276	20	1	13	227	20	4	19	468
10	1	10	513	15	2	12	347	20	1	14	287	20	4	20	515
10	2	<= 4	E	15	2	13	412	20	1	15	351	20	5	<= 9	E
10	2	5	69	15	2	14	478	20	1	16	410	20	5	10	2
10	2	6	141	15	2	15	529	20	1	17	468	20	5	11	12

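### Does an early stop under SAP step 2 conflict with the OBD definition when a tried dose is still admissible?

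*SAP*

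**What the plan says.** The SAP states that the "objective was to identify the OBD, defined as the dose that was admissible and had" the highest desirability. Protocol 4.1 likewise says that the admissible dosage with the highest estimated utility will be selected. Neither sentence limits the comparison to neighbouring levels or mentions early stops.

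Elimination is asymmetric. Under the SAP, if a dose is eliminated "due to toxicity, all doses higher than that dose would also be eliminated. The" same is not said of futility, which under Protocol 4.1 removes only the level concerned.

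Step 2 has two kinds of ending:

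- **Selection addressed.** Case A looks at levels j−1, j and j+1 (two levels at the ends of the range), and Case B at j and j−1. If all are E, the Case A instruction is to "stop the trial and no dose should be selected. In the case that" (the last words open the next sentence), and Case B ends in the same way.
- **Selection not mentioned.** The lowest-dose branch of Case B and both endings of Case C give only the instruction "at which point terminate the" trial.

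Step 3 opens with "Repeat step 2 until the maximum sample size of 60 is reached or if the number" on any one dose reaches 20. Only then does isotonic estimation pick the dose that is admissible "and that has the highest estimated utility". The conduct flowchart, Figure 1, is not reproduced in the text available here.

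**The concern.** Step 2 looks only at the current dose and its neighbours, whereas the OBD definition covers all admissible doses. If futility eliminates the doses in that window, a dose tried earlier can still pass both criteria when the trial ends. Cases A and B then report no dose although one meets the admissibility part of the definition. Case C and the lowest-dose branch of Case B appear to leave the conclusion open. The OBD is the trial's main result, so the fear is a conclusion that contradicts the plan's own definition, or one settled after the data are seen.

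**Working it through.** **Inputs.** From the documents: toxicity limit 0.15 with cutoff 0.95; efficacy limit 0.60 with cutoff 0.90; (λe, λd) = (0.118, 0.179); N* = 5; cohorts of 5; start at level 3 of 6; maximum 60 patients, or 20 on one dose. Assumed: a Beta(1,1) prior and the usual BOIN defaults φ1 = 0.6 × 0.15 = 0.09 and φ2 = 1.4 × 0.15 = 0.21.

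**Reproducing the plan's figures.**

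- λe = ln(0.91/0.85) / ln[(0.15 × 0.91)/(0.09 × 0.85)] = 0.0682/0.5790 = 0.118.
- λd = ln(0.85/0.79) / ln[(0.21 × 0.85)/(0.15 × 0.79)] = 0.0732/0.4097 = 0.179.
- For x events in n, the posterior is Beta(1+x, 1+n−x), so Pr(π < c) = P(Bin(n+1, c) ≥ x+1).
- Toxicity 1/5: Pr(πT > 0.15) = 0.85^6 + 6 × 0.15 × 0.85^5 = 0.776, admissible. Toxicity 2/5: add 15 × 0.15² × 0.85^4 = 0.176, giving 0.953, E.
- Efficacy 1/5: Pr(πE < 0.6) = 1 − 0.4^6 − 6 × 0.6 × 0.4^5 = 0.959, E. At 2/5 it is 0.821, at 4/5 0.233 and at 5/5 0.6^6 = 0.047, all admissible.

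All eight E limits in eTable 1 are reproduced (toxicity ≥2/5, 4/10, 5/15, 6/20; efficacy ≤1/5, 4/10, 6/15, 9/20).

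**Case split.** This is read from the text and the two boundaries because the flowchart is not shown. A rate up to 0.118 is Case A, between the boundaries Case B, and above 0.179 Case C. So 0/5 is Case A, 1/5 = 0.20 is Case C, and 2/15 = 0.133 is the only Case B result before the cap of 20.

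**Two paths that reach the situation.** Neither depends on a tie or an assumed event rate.

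| Path | Dosage 3 (DLT, efficacy) | Dosage 2 | Dosage 1 | SAP ending |
|---|---|---|---|---|
| 1 | 1/5, 5/5 (RDS 413): Case C, down | 1/5, 1/5 (E): Case C, down | 0/5, 1/5 (E): Case A | No dose; Dosage 3 still admissible |
| 2 | 1/5, 4/5 (RDS 308): Case C, down | 1/5, 4/5 (RDS 308): Case C, down | 1/5, 1/5 (E): Case C | Terminate; Dosages 2 and 3 still admissible |

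**How often.** The documents give no operating characteristics, so every rate here is an assumption. The Protocol's background cites infarct growth in up to 37% of patients, which gives a rough efficacy anchor of 1 − 0.37 = 0.63; that growth threshold is not stated. Steps 1–3 were simulated with 20,000 trials per setting, tie rule and seed, with DLT and efficacy independent. The table gives the share of trials stopping early with a tried, admissible dose.

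| Efficacy by dosage | DLT rate | Cases A/B, no dose | Endings silent on selection | Sum |
|---|---|---|---|---|
| Flat 0.63 | 5% | 0.6–0.7% | 0.6–1.0% | 1.2–1.7% |
| Flat 0.63 | 10% | 0.4–0.6% | 1.7–2.3% | 2.1–2.9% |
| Flat 0.70 | 10% | about 0.1% | 0.6–0.8% | 0.7–0.9% |
| 0.40, 0.55, 0.70, 0.55, 0.40, 0.40 | 5% | 6–8% | 3–5% | 9–13% |
| Same | 10% | 4–5% | 9–10% | 13–15% |
| 0.30, 0.40, 0.70, 0.40, 0.30, 0.30 (extreme) | 5% | 17–20% | 7–8% | 24–28% |

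At flat 0.63, a tried admissible dose remains in 48–59% of early stops with a 5% DLT rate and in 27–33% with 10%. If DLT instead rises from 2% to 25% across the six levels, the overall share is 1.4–1.9%.

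**What selecting at early stops would do (DLT 5%).**

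| Efficacy | Dose selected | No selection at early stops | Selection at every early stop |
|---|---|---|---|
| Flat 0.40 | A futile dose | 43–47% | 69–75% |
| Flat 0.50 | A futile dose | 78–82% | 90–93% |
| Only Dosage 3 effective | Dosage 3 | 61% | 83–85% |

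At flat 0.40 with DLT 10%, futile-dose selection goes from about 35–37% to 62–64%. At flat 0.40 with DLT 5%, 55–60% of the added selections rest on one cohort of 5.

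**The case for a change.** The best argument for a change is that neither reading makes the text fully tidy. If the step 2 rule overrides the general sentences, the endings in Case C and lowest-dose Case B still do not mention selection. If the general sentences fill that silence, they contradict Cases A and B. A line of text would cost little, and an efficacy curve peaking at one dose, which a dose-finding trial must allow for, makes the event far from rare.

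The unevenness of wording stands, and so do the two traced paths. The claim that the outcome is undetermined does not. Cases A and B give an explicit operating instruction, while the OBD sentence states an objective, and an objective can go unmet. Selection is tied to 60 patients or 20 on one dose, so a trial terminated in step 2 does not arrive there; the silent endings then mean the same as the explicit ones. The flowchart may say so, and its absence from the extracted text is not a gap in the plan. When the lowest dose is eliminated for toxicity, every higher dose goes with it and no conflict arises.

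Nor does added text offer a clear gain. Stating that no dose is selected would alter no result and would only write down the natural reading. Stating that a dose is selected would alter the design, with the costs tabulated above.

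**Conclusion.** No change follows. SAP step 2 can end the trial with a tried dose that still passes both criteria, and this sits awkwardly with the general OBD wording. Read in the ordinary way, with the specific stopping rule governing and step 3 applying only at its stated triggers, the plan gives one answer: no OBD is selected after an early stop. A competent report would describe that as no OBD selected, rather than as no admissible dose, and would show patients, DLTs and efficacy events for each tried dose in any case.

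The event affects about 1–3% of trials at flat efficacy 0.63 and under 1% at flat 0.70. It reaches 9–15% under an assumed moderate peak and 24–28% under an extreme one. Not selecting a dose is a defensible, conservative choice, because admissibility is a weak standard: 2/5 efficacy passes. Selecting at early stops would find a single effective dose more often but would also select futile doses more often. These figures rest on assumed event rates, independent DLT and efficacy, assumed handling of ties between untried doses, and a case split inferred without the flowchart.

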Red blood cell (RBC) count, white blood cell (WBC) count, neutrophil count, lymphocyte count, monocyte count, platelet (PLT) count, hemoglobin (Hb), creatinine (Cr)、Blood urea or urea nitrogen (BUN)、blood glucose (Glu)； prothrombin time (PT), activated partial thromboplastin time (APTT), international normalized ratio (INR)；						
6. Thrombolysis information: including drug name, infusion dosage and time, and occurrence of adverse events;						
7. Imaging: multimodal CT (including cranial NCCT, CTP, CTA), if CTP can be used for cranial CTA reconstruction, CTA examination can be omitted;						
8. Postoperative imaging: MRI must be done within 72 ± 24 hours. NCCT is completed 24 ± 12 hour, and other times as needed. MRA/CTA is completed within the follow-up time point and only needs						

to be done once.

9. Information on thrombectomy treatment, including but not limited to: anesthesia method, thrombectomy product information, reperfusion results after the first thrombectomy and final angiography, and the number of final mechanical thrombectomy;

10. The mRS score of the selected group refers to the score before the onset of the disease.

11. EQ-5D-5L: European Quality of Life Five Dimension Five Level Scale Questionnaire.

50 2 BACKGROUND AND SIGNIFICANCE

51 Despite the well-established benefit of endovascular thrombectomy (EVT) in acute
52 ischemic stroke (AIS) with large vessel occlusion (LVO), over half of patients remain
53 functionally dependent at 90-day follow-up¹⁻⁴. Efforts are increasing focus on
54 understanding the reasons for poor outcome and factors limiting the efficacy of EVT⁵.

55 Paradoxically, restoration of blood flow and reoxygenation can exacerbate tissue injury,
56 known as ‘reperfusion injury’^{6,7}. This type of injury occurs immediately after blood
57 flow restoration and is a major contribution to neurologic deterioration⁸⁻¹⁰. Recent
58 clinical studies have confirmed that up to 37% of thrombectomy patients experience
59 infarct lesion growth despite successful vascular recanalization, which is significantly
60 associated with poor prognosis¹¹.

61 Ischemic postconditioning conventionally refers to a series of brief blood vessel
62 occlusions and reperfusions, which may induce an endogenous neuroprotective effect
63 and reduce cerebral ischemia/reperfusion injury¹². It has demonstrated that remote
64 ischemic postconditioning can improve 3-month functional outcomes in patients with

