65 moderate AIS^{13,14}, but this finding was not confirmed by other reports^{15,16}. The delay
66 of remote ischemic postconditioning initiation after thrombolysis can’t protect from the
67 reperfusion injury. Rapid local ischemic postconditioning (RL-IPostC) , referring to the
68 intervention promptly initiated after the onset of reperfusion that directly modulates the
69 rapid augmentation of blood flow during reperfusion, may theoretically attenuate
70 reperfusion injury. Previous reports have demonstrated neuroprotective effects in
71 animal models of cerebral ischemia¹⁷⁻²⁰, yet remain unproven in clinical practice. With
72 the widespread application of EVT for revascularization in LVO-AIS, RL-IPostC can

73 now be rapidly and conveniently implemented. Recent studies indicate that RL-IPostC
74 is feasible and well-tolerated in AIS patients undergoing EVT, suggesting it could be a
75 promising therapy to mitigate cerebral ischemia-reperfusion injury²¹⁻²³. The most
76 effective ischemic postconditioning protocol, has yet to be identified.

77 **3 STUDY OBJECTIVES**

78 To determine the safety and efficacy of RL-IPostC on LVO-AIS of successful
79 thrombectomy, and the optimal dosage of RL-IPostC.

80 **4 STUDY DESIGN AND MANAGEMENT OVERVIEW**

81 **4.1 Study design overview**

82 The study is an investigator-initiated prospective, adaptive, multicenter clinical trial. It
83 employs the Bayesian Optimal Interval Phase I/II (BOIN12) trial design to assess the
84 safety and determine the optimal dosage of ischemic postconditioning intervention. The
85 BOIN12 design facilitates decisions regarding dosage escalation and de-escalation by
86 simultaneously taking account of toxicity and efficacy. It quantifies the desirability of
87 a dosage in terms of toxicity-efficacy trade-off. Within the BOIN12 framework,
88 patients are adaptively assigned to the most desirable dosage, balancing optimal toxicity
89 and efficacy. The rank-based desirability score (RDS) can be pre-tabulated before the
90 trial commences using the quasi-beta-binomial model²⁴. In this trial, the following
91 toxicity-efficacy trade-off utilities are established for calculating the RDS: (No Toxicity,
92 Efficacy) = 100; (Toxicity, Efficacy) = 60; (No Toxicity, No Efficacy) = 40; (Toxicity,
93 No Efficacy) = 0. The RDS table will be detailed in statistical analysis plan.

94 Stopping criteria are implemented to prevent the allocation of patients to dosage that is

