95 severely toxic or ineffective. BOIN12 utilizes two dosage-acceptability criteria to
96 determine which dosage may be administered. If the probability of a toxicity outcome
97 exceeding the upper limit of toxicity 0.15 is greater than 0.95, then dosage level and
98 higher are eliminated from the trial. Conversely, if the probability of an efficacy

99 outcome falling below the lower limit of efficacy 0.60 is more than 0.90, then dosage
100 level is removed from consideration. The dosage that is both admissible and has the
101 highest estimated utility will be selected as the optimal dosage.

102 **4.2 Blinding**

103 Although the treatment medications are known to the patients and the treating
104 neurointerventionist, the study employs a blinded assessment. Investigators responsible
105 for follow-up neurological evaluations, as well as the independent Clinical Events
106 Committee (CEC), are kept unaware of treatment group assignment to maintain
107 objectivity. These assessors have no role in patient care.

108 **4.3 Study milestones**
109 A 16-month budget and recruitment plan have been planned; the key study milestones
are shown in the table below.

STUDY MILESTONES

Pre-enrollment study initiation	2 months
Recruitment and follow-up	9 months
Completion of follow-up	3 months
Data analysis and publication	2 months
Total duration	16 months

110 This schedule is preliminary and may be adjusted based on the progress of the study.

111 **4.4 Site recruitment**

112 Six National Comprehensive Stroke Centers will be designated as trial sites. Selection
113 will be based primarily on the following criteria: (1) prior experience in multicenter
114 clinical trials; (2) an annual volume of no fewer than 50 endovascular thrombectomy
115 procedures for AIS over the past three years; and (3) routine use of a balloon guide
116 catheter in these procedures.

117 **4.5 Site training, certification, and updates.**

118 All investigators are required to complete the following training modules and receive
119 certification:

120 ● Study procedures
121 ● Primer on the diagnosis of ischemic stroke.
122 ● Rapid-SAVE eligibility
123 ● Modified Rankin Scale score
124 ● NIHSS

125 Successful completion of the training program and approval from the local Institutional
126 Review Board (IRB) for human research will be required before a site can be certified
127 to enroll patients. Intermittent web-based meetings with the principal investigator and

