260 performed if necessary, local arterial dissection should be observed in light cases, and
261 stent implantation should be performed in severe cases.

262 7.4 AE Reporting

263 Once an adverse event (including serious adverse events) occurs, the time of occurrence
264 of the adverse event, clinical manifestations, treatment process and duration, outcome
265 and relationship with the drug should be recorded in detail on the case report form. If
266 there are abnormal laboratory tests, the patient must be followed until the test results
267 return to normal. Serious adverse events should be completed and reported to the
268 investigator, the Ethics Committee (EC)within 24 hours after being notified.

269 The CEC consists of three experts, two neurointerventionists and a neurologist. The
270 committee will assess all complications that occur during the course of the study and
271 classify the severity and relevance according to the definitions in the Adverse Events
272 (AEs) section. The CEC may request any relevant images and information required for
273 the AE determination.

274 8 STATISTICAL CONSIDERATIONS

275 8.1 Sample size estimates

276 This maximum sample size of 60 and 12 cohorts, with a sample size of 5 for each cohort.

277 8.2 Statistical analysis plans

278 Details in supplementary material of statistical analysis plans (SAP).

279 8.3 Data safety monitoring plan

280 The independent Data and Safety Monitoring Board (DSMB) is composed of
281 experienced two neurologists and one biostatistician who are neither directly involved
282 in the study. The DSMB meets before the study initiation and during the study as
283 required to reviews structured open-ended reports provided by research statisticians.
284 The DSMB is responsible for making recommendations to the Executive Committee on
285 the dosage escalation and deescalation, cessation or continuation of the study. In
286 addition, the DSMB will review the occurrence of SAEs and make recommendations
287 on the safety of the trial to continue, stop, or modify the study protocol.

288 9 ETHICAL AND REGULATORY STANDARDS

289 9.1 Ethical considerations

290 This clinical study must be conducted in accordance with the requirements of the
291 Declaration of Helsinki and other relevant regulations. Before the study begins, the
292 study protocol and informed consent form (ICF) and other documents must be approved
293 by the Ethics Committee of the research center before the study can be conducted.

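### Should the trial run to 60 patients instead of ending once any dose has 20?

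*SAP*

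**What the plan says.** SAP step 3 repeats the dose-assignment step until 60 patients have been treated, or until the number "of patients treated on any dose reaches 20. Then, use the isotonic estimation" is used to select the optimal dose. It is the rule that ends the trial.

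Protocol 8.1 gives the size as a ceiling: "This maximum sample size of 60 and 12 cohorts, with a sample size of 5 for each cohort". Protocol 8.2 hands the rest to the SAP: "Details in supplementary material of statistical analysis plans (SAP". The Synopsis speaks of a total of 60 and limits each dosage level to 20 patients, without saying whether reaching 20 closes that level or the trial.

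SAP step 2 guards against settling too early: "dose, an extra dose exploration rule is implemented to escalate to the next" higher untried level. One condition is "The number of patients treated at the current dose is" 15 or more. Protocol 4.1 removes a dose for futility if the probability of an efficacy "outcome falling below the lower limit of efficacy 0.60 is more than 0.90, then dosage" level is dropped. eTable 1 stops at 20 patients per dose, in line with step 3.

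**The concern.** The selected dose is the main result; Protocol section 3 names safety, efficacy in successful "thrombectomy, and the optimal dosage of RL-IPostC" as the objectives. A stop at 20 on one dose can end the trial well short of 60. The exploration rule acts at 15 patients, one cohort before the stop. If the design tries the next dose and then returns, the trial ends at 15 + 5 + 5 = 25 patients, with the new dose judged on five.

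Two errors could become more frequent: missing the best dose, and naming an optimal dose when none reaches the 0.60 floor. Neither document reports selection probabilities or expected sample size, so a reader cannot see the size of either.

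**Working it through.** **Reproducing the plan's figures.** With φ = 0.15, φ1 = 0.6φ = 0.09 and φ2 = 1.4φ = 0.21, the standard BOIN boundaries are:

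- λe = ln[(1−φ1)/(1−φ)] / ln[φ(1−φ1)/(φ1(1−φ))] = ln(0.91/0.85) / ln(0.1365/0.0765) = 0.1178
- λd = ln[(1−φ)/(1−φ2)] / ln[φ2(1−φ)/(φ(1−φ2))] = ln(0.85/0.79) / ln(0.1785/0.1185) = 0.1787

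These match the printed 0.118 and 0.179. Beta(1,1) posteriors give elimination for toxicity from 2/5, 4/10, 5/15 and 6/20, and for efficacy up to 1/5, 4/10, 6/15 and 9/20, as in eTable 1. Desirability taken as Pr(Beta(1+x, 1+n−x) > 0.85), with x = 0.6·Eff + 0.4·(n−Tox), reproduces the order of all 144 numeric entries in eTable 1. The simulated design is therefore the written one.

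**Assumptions.** The documents give no true rates. Assumed: DLT 5% at every dose; efficacy 0.85 at the best dose, 0.75 one level away, 0.67 two away and 0.63 elsewhere. The 0.63 is 1 − 0.37, from the background statement that "clinical studies have confirmed that up to 37% of thrombectomy patients experience" infarct growth; using it as a background rate is itself an assumption. Ties are broken at random. The final choice is the admissible tried dose with the highest 60·pE + 40·(1−pT), with pE the observed rate and pT isotonic.

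**Three endings.** Step 3 as written; the same design run to 60 with no per-dose limit; and the other reading of the Synopsis, where a dose closes at 20 and the trial continues (closed dose skipped, nearest open dose next, which is an assumption). The last column is the mean true efficacy of the selected dose, step 3 → no limit.

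| Best dose | Selected: step 3 | No limit | Dose closes at 20 | Mean true efficacy (%) |
|---|---|---|---|---|
| 1 | 17% | 24% | 44% | 71.2 → 72.6 (+1.4) |
| 2 | 27% | 33% | 37% | 75.9 → 76.5 (+0.6) |
| 3 | 68% | 70% | 64% | 81.3 → 81.5 (+0.2) |
| 4 | 38% | 44% | 52% | 76.7 → 77.4 (+0.7) |
| 5 | 16% | 25% | 31% | 70.4 → 72.3 (+1.9) |
| 6 | 9% | 15% | 23% | 66.9 → 68.5 (+1.6) |

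Mean enrolment is 28–36 under step 3 and 58–60 with no limit. Removing the stop gains 24−17 = 7, 6, 2, 6, 9 and 6 points in exact selection. A smoothed efficacy estimate raises the largest efficacy gain from 1.9 to 2.3 points.

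**All doses equally ineffective, DLT 5%: a dose is still named.**

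| True efficacy | Step 3 | No limit |
|---|---|---|
| 0.30 | 10–11% | 3% |
| 0.40 | 44% | 24% |
| 0.50 | 80% | 68% |
| 0.55 | 90% | 84% |

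At 0.40, closing only the dose that reaches 20 gives about 31–37%.

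**Sensitivity.** With the best dose other than Dosage 3, 25 scenarios (other DLT rates, steeper peaks) give gains of 1 to 19 points from removing the stop; with Dosage 3 best, −1 to +3. Over 600 random scenarios (best 0.75–0.90, others 0.40–0.70) the best dose is selected in 43% under step 3, 51% with no limit and 50% if a dose closes at 20, with mean enrolment of 33, 57 and 49.

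**The case for a change.** The strongest case for a change is that the direction is consistent and 60 patients are already planned. Whenever the best dose is not Dosage 3, step 3 selects it less often, and at 40% efficacy everywhere it names a dose 44/24 = 1.8 times as often. Steeper peaks cost more. With the best dose at 0.85 and the others at 0.50–0.70, selection of Dosage 1 rises from 30% to 49% without the stop; 19 points times an efficacy gap of 0.15 to 0.35 is roughly 3 to 7 points of efficacy. That stands, as does the absence of operating characteristics.

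Four things limit it.

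- Most of the low accuracy away from Dosage 3 comes from the one-level search and remains at 60 patients: with Dosage 6 best, 9% becomes only 15%.
- The 1.8-fold figure needs a comparator with no per-dose limit, which neither document describes. Against closing only the full dose it is about 1.2 to 1.4. It also needs 40% efficacy at all six doses, 63 − 40 = 23 points below the assumed background. At 0.55 the contrast is 90% against 84%, so naming a dose just under the floor is common with or without the stop.
- Removing every limit is not clearly the better remedy. For five of the six best-dose positions above, closing the dose at 20 selects better.
- The SAP is written in the past tense. If data have been seen in this open-label adaptive trial, changing the ending rule would bring its own risk of bias.

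**Conclusion.** No change follows. The stop buys a trial of roughly half the size, about 24 to 32 fewer patients on average. Under the graded efficacy rates it costs about 6 to 9 points in exact selection when Dosage 3 is not best, about 2 points when it is, and at most about 2 points of true efficacy in the dose chosen. The price is higher with steeper peaks and lower with flatter ones. A sponsor may reasonably accept that in an early dose-finding trial whose elimination rules are unaffected.

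No stated figure is missed: Protocol 8.1 and the SAP both give 60 as a maximum, and no selection probability is promised. The Synopsis is looser in calling 60 a total and in leaving open what reaching 20 does. But step 3 never puts more than 20 patients on a dose, so it respects that cap, and Protocol 8.2 makes the SAP the place for the detail. A table of operating characteristics would help readers of the report, but would not alter how step 3 assigns patients or selects the dose.

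All sizes rest on assumed true rates, on the tie-break and final efficacy estimate chosen, and, for the third ending, on an assumed rule for skipping a closed dose.
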